Post-acute Care Preferred Provider Network Skilled Nursing Facility Selection as a Function of Repisodic Mobile Application Settings

Statistical Analysis Plan

February 16, 2023

Statistical Analysis Plan

Brief Summary

This study tests whether changing the relative order of presentation of post acute care skilled nursing facilities (SNFs) in the Repisodic application, i.e., presenting preferred SNFs (P-SNFs) first, increases selection of, and discharges to, P-SNFs and decreases lengths of stay (LoS) for Geisinger patients discharged to SNFs. Along with the order of P-SNFs, the study also assesses whether a short video reviewing the benefits of care coordination in P-SNFs increases patient election to transfer to one.

Randomization

Case managers were randomized to one of two conditions upon their account creation (Default List vs. P-SNF Top-Sorted List). Patients were independently randomized to one of two conditions when Repisodic lists were generated for them (Full List/Full Map/Default Video vs. P-SNF List/P-SNF Map/P-SNF Video).

Project Status

All interventions were launched on 5/28/2021 and data collection is ongoing. Outcome data have not been examined as a function of experimental condition. However, only patients who are ultimately discharged to a SNF can be included in our analyses, and not all randomized patients are ultimately discharged to SNFs (e.g., patients who were discharged home, despite initially being considered for a SNF). So, to assess enrollment progress throughout the study, we need to extract data on patients' discharge locations and remove patients who were not discharged to a SNF.

Our original primary outcome time frame was 12 months or as long as it takes to reach N=4,000, whichever occurs first. However, we decided to extend our outcome time frame to 24 months or as long as it takes to reach N=5,000 patients. We made this change because we noticed an imbalance in the number of case managers assigned to the two conditions, such that by chance, there were more active case managers in the P-SNF top-sorted condition (N = 104 as of 1/2/23) compared with the default list condition (N = 70 as of 1/2/23). We ran a simulation power analysis to reassess how many patients should be in our final sample size, given the imbalance in case manager assignment, and determined that 5,000 patients would yield sufficient power to detect a 4% increase in P-SNF selection.

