However, by the time we made the decision to change our inclusion criteria, enrollment exceeded 5,000 patients. We plan to include all eligible patients enrolled through 1/2/23 in analyses, because we have already pulled enrollment data on these patients.

Power Analysis

Data will be collected from 5,000 patients who were discharged to SNFs. We expect to have 80% power to detect a 4% increase (34% to 38%) in selection of P-SNFs at two-tailed p < .05.

Analysis Approach

Analyses described below represent our planned analyses assuming statistical assumptions are met. If assumptions are not met, we will run alternative tests appropriate for the outcome distribution (e.g., non-parametric tests).

Recent work suggests that OLS regressions are appropriate in randomized experiments with binary outcome variables such as ours (Gomilla, 2021). Therefore, for binary outcome variables, we default to running OLS regressions.

Some of our originally preregistered outcome descriptions mentioned comparing Time 1, before the Repisodic app was deployed, to Time 2, during the study, after launch of the app. Upon learning that it is infeasible to obtain comparable Time 1 measurements and include them in analysis, we decided to omit Time 1 to focus analyses entirely on comparing outcomes during the study period (i.e., the primary causal investigation).

Primary Outcomes

P1: Overall LoS (system/case manager level) [Time Frame: 24 months or as long as it takes to reach N=5,000, whichever occurs first]

Difference in LoS (in days) for patients as a function of case manager study condition

Analysis: We will run a gamma regression to test whether LoS differs between patients with a case manager in Default List versus P-SNF Top-Sorted groups.

P2: P-SNF placement (system/case manager level) [Time Frame: 24 months or as long as it takes to reach N=5,000, whichever occurs first]

Difference in proportion of discharges of patients to P-SNFs (out of P-SNFs + NP-SNFs) as a function of case manager study condition.

Analysis: We will run a beta regression to test whether there is a difference in the proportion of patient discharges to P-SNFs for the case manager Default List and P-SNF Top-Sorted groups.

P3: P-SNF pre-selection (case manager level) [Time Frame: 24 months or as long as it takes to reach N=5,000, whichever occurs first]

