Number of P-SNFs selected by case managers for inclusion in the patients' lists, to assess the direct impact of Repisodic changes on case manager behavior; this is the first decision in the process, before patients' selections and SNF availability factor into the final discharge decision and placement.

Analysis: We will run a negative binomial regression to test whether the number of P-SNFs preselected differs as a function of case manager study arm, clustering standard errors at the case manager level. P4: P-SNF selection (case manager level) [Time Frame: 24 months or as long as it takes to reach N=5,000, whichever occurs first]

Number of P-SNFs selected by patients to help assess the downstream impact of Repisodic changes on patient behavior following case manager pre-selection, again omitting the influence of SNF availability.

Analysis: We will run a negative binomial regression to test whether the number of P-SNFs selected differs as a function of case manager condition, clustering standard errors at the case manager level.

Note: Retrospective data prior to the study period suggested that only ~15% of patients indicate their selections in the Repisodic app. Therefore, data will be missing for many patients in this analysis. However, we will run this analysis on patients with available data.

P5: P-SNF percent selected (case manager level) [Time Frame: 24 months or as long as it takes to reach N=5,000, whichever occurs first]

Percentage of patients who selected at least one P-SNF, to help assess the downstream impact of Repisodic changes on patient behavior following case manager pre-selection.

Analysis: We will run a beta regression to test whether the percentage of patients who selected one or more P-SNFs differs as a function of case manager condition, clustering standard errors at the case manager level.

Note: Retrospective data prior to the study period suggested that only ~15% of patients indicate their selections in the Repisodic app. Therefore, data will be missing for many patients in this analysis. However, we will run this analysis on patients with available data.

P6: LoS (patient/caretaker level) [Time Frame: 24 months or as long as it takes to reach N=4,000, whichever occurs first]

LoS for patients (in days).

Analysis: We will run a gamma regression to test whether LoS differs as a function of patient condition, clustering standard errors at the case manager level.

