P7: P-SNF placement (patient/caretaker level) [Time Frame: 24 months or as long as it takes to reach N=5,000, whichever occurs first]

Patient was discharged to a P-SNF: yes/no.

Analysis: We will run an OLS regression to test whether patient P-SNF placement rates differ as a function of patient condition, clustering standard errors at the case manager level.

P8: P-SNF selection (patient/caretaker level) [Time Frame: 24 months or as long as it takes to reach N=5,000, whichever occurs first]

Patient selected a P-SNF for discharge: yes/no. This is a more direct reflection of patient behavior, not yet moderated by bed availability and other real-world considerations that affect Outcome 7.

Analysis: We will run an OLS regression to test whether patient P-SNF selection rates differ as a function of patient condition, clustering standard errors at the case manager level.

Note: Retrospective data prior to the study period suggested that only ~15% of patients indicate their selections in the Repisodic app. Therefore, data will be missing for many patients in this analysis. However, we will run this analysis on patients with available data.

Secondary Outcomes

S1: Time to pre-select a SNF (case manager level) [Time Frame: 24 months or as long as it takes to reach N=5,000, whichever occurs first]

Time to pre-select a SNF/SNF list in Repisodic (in minutes), from the time that the case manager first signs into the iPad to when the case manager saves the list to send to the patient. This measure excludes cases in which the task was not completed.

Analysis: We will run an OLS regression to test whether the time to pre-select a SNF list in Repisodic differs as a function of case manager condition, clustering standard errors at the case manager level.

S2: Time to select a SNF (patient/caretaker level) [Time Frame: 24 months or as long as it takes to reach N=5,000, whichever occurs first]

Time to select a SNF in Repisodic (in minutes), from the time that the patient first signs or is signed into the iPad to when the patient clicks to send the list to the case manager. This measure excludes cases in which the task was not completed.

Analysis: We will run an OLS regression to test whether the time to select a SNF list in Repisodic differs as a function of patient condition, clustering standard errors at the case manager level.

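### P1 compares patients' length of stay between arms randomised by case manager but plans no allowance for clustering, so its type I error exceeds 5% for any positive within-manager correlation

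*SAP*

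**What the plan says.** Under Randomization, "Case managers were randomized to one of two conditions upon their account creation"; patients are randomised separately to the list, map and video conditions. Project Status reports "more active case managers in the P-SNF top-sorted condition (N = 104 as of 1/2/23") against 70 in the default list condition.

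Under Primary Outcomes, P1 is length of stay (LoS) in days for patients, by the case manager's condition. The analysis is a "gamma regression to test whether LoS differs between patients with a case manager in Default List versus P-SNF Top-Sorted groups". Nothing more is said about its standard errors.

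Other outcomes do state the error structure:

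- P6, the same outcome and model for the patient-level factor: "gamma regression to test whether LoS differs as a function of patient condition, clustering standard errors at the case manager level".
- P3, the same randomised factor as P1: "number of P-SNFs preselected differs as a function of case manager study arm, clustering standard errors at the case manager level".
- S1, again the same factor: "time to pre-select a SNF list in Repisodic differs as a function of case manager condition, clustering standard errors at the case manager level".
- P4 and P5 test the same factor and also cluster on case manager.

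Analysis Approach has no general sentence on clustering. If assumptions fail, it promises "alternative tests appropriate for the outcome distribution", which concerns distributional shape and not dependence between patients.

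**The concern.** The Default versus Top-Sorted comparison is cluster-randomised. A manager's habits, unit and case mix can make LoS more alike among that manager's patients than across managers. Because they are all in one arm, that shared variation goes straight into the difference between arms. A plain gamma regression on patient rows does not see it and computes its standard error as if about 5,000 independent patients had been randomised.

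P1 is one of eight primary outcomes and the only LoS test of the case-manager intervention; shortening LoS is among the aims in the Brief Summary. An understated standard error makes the p-value too small and the interval too narrow, and a false positive would support a headline claim. The plan protects P6, whose factor is randomised by patient and where clustering usually matters less, but not P1, where it matters most.

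**Working it through.** **1. Count of the planned analyses.** There are 13 regressions: P1 to P8, S1, S2 and O1 to O3. Eleven specify standard errors clustered on case manager. The two that do not are P1 and P2.

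**2. The plan's own figure.** The SAP has no sample-size calculation for LoS. Its only design figure is 80% power for 34% versus 38% P-SNF selection with 5,000 patients. A simple two-proportion calculation split 70:104 gives 82.3% (81.6% with continuity correction), and 80.3% with an ICC of 0.002. The stated power is therefore plausible, but it says nothing about P1.

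**3. Inputs.**

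- Patients: 5,000 (Power Analysis; Project Status says enrolment went beyond this).
- Case managers: 104 + 70 = 174, active on 1/2/23 (Project Status).
- Mean caseload: m = 5000/174 = 28.7.
- Nominal two-sided level: 5% (stated for P-SNF selection).
- ICC of LoS and coefficient of variation (CV) of caseload: not in the SAP; ranges assumed.

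**4. Formulas.**

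- Design effect: DEFF = 1 + ((1 + CV²)·m − 1)·ICC.
- True type I error of the unclustered test: 2·(1 − Φ(1.96/√DEFF)).

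Example, equal caseloads and ICC 0.01: DEFF = 1 + 27.7 × 0.01 = 1.277; 1.96/√1.277 = 1.734; error = 8.3%.

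**5. Results.** True type I error at nominal 5%:

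| ICC | DEFF, CV 0 | Error, CV 0 | Error, CV 0.5 | DEFF, CV 1 | Error, CV 1 |
|---|---|---|---|---|---|
| 0 | 1 | 5.0% | 5.0% | 1 | 5.0% |
| 0.001 | 1.028 | 5.3% | 5.4% | 1.056 | 5.7% |
| 0.005 | 1.139 | 6.6% | 7.1% | 1.282 | 8.3% |
| 0.01 | 1.277 | 8.3% | 9.2% | 1.565 | 11.7% |
| 0.02 | 1.555 | 11.6% | 13.3% | 2.129 | 17.9% |
| 0.05 | 2.387 | 20.5% | 23.7% | 3.824 | 31.6% |

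If only 120 managers contribute patients (assumed; m = 41.7, equal caseloads), the errors at the five non-zero ICCs are 5.5%, 7.4%, 9.8%, 14.6% and 26.0%.

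**6. Check on the planned model.** P1 was simulated as a log-link gamma regression with 70 versus 104 managers, 5,000 patients, gamma-distributed manager effects, patient-level gamma shape 1.5 (assumed) and 10,000 runs per setting:

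| ICC | Unclustered, CV 0 | Unclustered, CV 1 |
|---|---|---|
| 0.001 | 5.2% | 5.6% |
| 0.005 | 6.3% | 8.1% |
| 0.01 | 8.2% | 11.4% |
| 0.02 | 11.0% | 17.8% |
| 0.05 | 21.4% | 31.5% |

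With case-manager-clustered standard errors the range was 5.1–5.6% (CV 0) and 5.5–6.1% (CV 1). At ICC 0 the unclustered test gave 5.1%, so the excess comes from within-manager correlation and not from the gamma model. A second simulation, with a different gamma variance and caseload CV of 0 and 0.8, agreed: at ICC 0.05 the unclustered error was 19.8% and 29.0%, against 5.0% and 5.8% with clustering.

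**The case against.** The best counter-reading starts from the headings. P1 and P2 alone are labelled as system/case manager level, and they are exactly the two analyses without the clustering phrase. Perhaps both were meant to be run on data aggregated by manager. For P2 that is plausible: its "beta regression to test whether there is a difference in the proportion of patient discharges to P-SNFs for the case manager Default List" group and the Top-Sorted group does not state its unit, and with one proportion per manager the problem largely disappears, so no error-rate claim is made about P2. For P1 the reading does not hold. Both its outcome and its analysis sentence refer to patients, and no aggregation is described.

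It can also be said that the SAP is silent on P1's standard errors rather than committed to naive ones, and that analysts who cluster everywhere else would probably cluster here too. That is likely, and the gap looks like a drafting omission. But clustering is specified outcome by outcome, so an analyst following the text has no instruction to apply it to P1.

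Two points on size stand. Nothing in the SAP places the ICC within the assumed range, and at ICC 0.001 the excess is trivial. There the remedy brings no visible gain, since the clustered test itself reaches 5.5–6.1% when caseloads are very uneven. Also, 174 is the number of managers active on 1/2/23; the number randomised is not given.

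**Conclusion.** The concern holds, and P1 must be corrected. As written, it analyses a cluster-randomised comparison as if patients were independent, against the plan's own practice in 11 of 13 regressions. The direction is certain: with a mean caseload above one, DEFF exceeds 1 for any positive ICC. The size is conditional on the assumed ICC and caseload spread. At 174 managers it runs from 5.3% (ICC 0.001, equal caseloads) to 31.6% (ICC 0.05, CV 1), with 8.3% to 11.7% at ICC 0.01.

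**What to change.** In the P1 analysis paragraph, specify that the gamma regression uses standard errors clustered by case manager, in the wording already used for P6. Project Status says outcomes had not been examined by condition, so a change made while that is still true cannot be driven by results.

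The cost is one phrase and a wider interval; no new data are needed. The standard error grows by √DEFF. With equal caseloads the factor is about 1.01 at ICC 0.001, 1.13 at 0.01 and 1.54 at 0.05. With caseload CV 1 it is about 1.03, 1.25 and 1.96. The loss of apparent precision can therefore be substantial, but that precision was never in the design.

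### P2 applies beta regression to a contrast randomised by case manager without stating unit of analysis, weights or clustering, and the method suits neither patient rows nor manager proportions well

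*SAP*

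**What the plan says.** SAP, Randomization: "Case managers were randomized to one of two conditions upon their account creation". The case manager is therefore the randomised unit for every comparison of Default List with P-SNF Top-Sorted List.

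SAP, Primary Outcomes, P2 defines the outcome as the difference between those arms in the share of patient discharges that go to P-SNFs. The analysis sentence is "We will run a beta regression to test whether there is a difference in the proportion of patient discharges to P-SNFs", followed only by the names of the two arms. It mentions no unit of analysis, weights or clustering.

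P5, also a case-manager contrast, uses the same model family but adds the adjustment: the test is "whether the percentage of patients who selected one or more P-SNFs differs as a function of case manager condition, clustering standard errors" at the case-manager level. P3, P4 and S1 do likewise. For the same placement outcome by patient arm, P7 says "We will run an OLS regression to test whether patient P-SNF placement rates differ as a function of patient condition", again with clustering by case manager. Analysis Approach names OLS as the default for binary outcomes. Its fallback for failed assumptions concerns tests suited to the outcome distribution and does not mention clustering.

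**The concern.** P2 is the primary placement outcome for the case-manager intervention. Patients of one manager share that manager's habits and local SNF supply, so their placements are likely to be correlated, and the arm was assigned to the manager. A valid test must either adjust its standard errors for this or work on one summary per manager. P2 states neither.

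The reader is left with two layouts, and beta regression is awkward in both. On patient rows it cannot be fitted, and a substitute model without clustering would give too small a standard error. On manager proportions, equal weighting answers a different question from the one P2 states, and managers at exactly 0% or 100% need a rule that the SAP does not give. At stake is whether a claimed effect on placement has the error rate and the meaning that the plan assigns to it.

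**Working it through.** **Inputs.**
- Case managers: 104 + 70 = 174 active as of 1/2/23 (Project Status).
- Patients: "Data will be collected from 5,000 patients who were discharged to SNFs" (Power Analysis). Mean caseload m = 5,000 / 174 = 28.7. Enrolment later passed 5,000, so the true mean may be a little higher.
- Rate: 34%, which Power Analysis gives for selection of P-SNFs. Its use for placement is an assumption.
- ICC and caseload spread: not in the SAP. All values below are assumptions.

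**The plan's own figure.** There is none for P2. The nearest is 80% power for 34% against 38%. If patients split as managers do (70:104, so about 2,011 and 2,989), a two-proportion test without clustering has 82.3% power, or 81.5% with continuity correction. A design effect of 1.062 brings it to 80%, which is an ICC of 0.062 / 27.7 = 0.002. The SAP gives neither the ICC nor the model of its simulation, and the figure concerns selection, so it does not settle how P2 is to be analysed.

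**The analyses side by side.**

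| Outcome | Randomised unit | Model | Clustered by case manager? |
|---|---|---|---|
| P1 LoS | case manager | gamma | not stated |
| P2 placement | case manager | beta | not stated |
| P3, P4 counts | case manager | negative binomial | yes |
| P5 percent selecting | case manager | beta | yes |
| S1 time | case manager | OLS | yes |
| P7 placement | patient | OLS | yes |

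P6, P8, S2 and O1 to O3 also cluster. P1 and P2 are the only exceptions.

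**Layout A: one row per patient.** Placement is 0/1. The beta density is defined strictly between 0 and 1, so the named model cannot be fitted. For any patient-level substitute without clustering, with equal caseloads:

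DEFF = 1 + (28.7 − 1) × ICC; true two-sided error = 2 × [1 − Φ(1.96 / √DEFF)].

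With unequal caseloads of coefficient of variation CV, DEFF = 1 + [(1 + CV²) × 28.7 − 1] × ICC.

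| Assumed ICC | DEFF, equal | Error, equal | DEFF, CV 0.8 | Error, CV 0.8 |
|---|---|---|---|---|
| 0.01 | 1.28 | 8.3% | 1.46 | 10.5% |
| 0.05 | 2.39 | 20.5% | 3.31 | 28.1% |
| 0.10 | 3.77 | 31.3% | 5.61 | 40.8% |

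**Layout B: one proportion per manager.** The within-manager correlation is absorbed into the spread of the proportions. Two problems remain.

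1. *Weights.* Unweighted, a manager with 2 patients and one with 100 count one half each. In a proportion of patient discharges they would count 2/102 = 2% and 98%.
2. *Boundary values.* With binomial variation only, the chance of a proportion of exactly 0 or 1 is 0.66ⁿ + 0.34ⁿ. For n = 5 this is 0.125 + 0.005 = 13%; for n = 10 it is 1.6%; at 28.7 it is below 0.001%.

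Null simulations of Layout B (70 and 104 managers, 34% rate, proportions pulled slightly inwards so that the model could be fitted, 1,500 replicates) gave these rejection rates at nominal 5%:

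| ICC | Equal caseloads, model-based SE | CV 0.8, model-based SE | CV 0.8, robust SE |
|---|---|---|---|
| 0.01 | 5.7% | 10.6% | 5.9% |
| 0.05 | 5.0% | 9.1% | 5.5% |
| 0.10 | 7.9% | 9.2% | 6.6% |

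In a separate run of 600 replicates per setting, with CV 0.8, between 5.4% and 7.6% of proportions were exactly 0 or 1 over these ICCs.

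**The alternative.** In that 600-replicate run, patient-level OLS with standard errors clustered by case manager rejected about 4% to 8% of the time across all settings tried. Monte Carlo error is about √(0.05 × 0.95 / 600) = 0.9 points.

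**The case against.** The strongest reply is that P2 is labelled system/case manager level and names a model for proportions, while the SAP sends binary patient data to OLS. The natural reading is then one proportion per manager, for which no clustering term is needed. P5 does not refute this: clustering on manager with one row per manager amounts to a heteroscedasticity-robust standard error, so its extra phrase may be only uneven wording. Equal weighting of managers is also a recognised cluster-level estimand, and boundary proportions could be handled under the fallback for failed assumptions.

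Much of this stands. A reader might infer that the P2 p-value is invalid under either layout, or that the planned test has a false-positive rate of up to 31%. The SAP supports neither inference. The 8% to 31% range describes a patient-level test without clustering, which cannot be the beta regression that P2 names. On manager proportions with near-equal caseloads the test is close to nominal. Nor does the SAP say that low-volume managers will be dropped.

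Three things survive. Aggregation is nowhere stated. P2's own definition, a proportion of patients' discharges, leans towards a patient-weighted quantity that an unweighted manager-level model does not estimate. And the fallback names no specific remedy for boundary values and is silent on weights and clustering.

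**Conclusion.** The concern holds in this form: P2 leaves its unit of analysis, weights and standard errors open, departs from the clustering stated in P3, P4, P5 and S1, and names a model that suits neither layout well.

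On patient rows the model cannot be fitted, and a substitute without clustering would have error of about 8% to 31% at nominal 5% (assumed ICC 0.01 to 0.10, equal caseloads of 28.7).

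On manager proportions the lack of clustering does not invalidate the p-value. The faults are equal weighting against a patient-level definition, and unusable values of 0% and 100%. Their size depends on caseloads that the SAP does not report: at an assumed 34% rate, boundary values affect about 13% of managers with 5 patients, 1.6% with 10 and almost none at 28.7. The inflation to about 9% to 11% seen with model-based errors rests on an assumed caseload CV of 0.8 and falls to about 5% to 7% with robust errors. Assignment at account creation makes unequal caseloads likely, but the SAP does not show them.

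This is more than a missing detail, because the SAP already has a better-fitting method for the same outcome.

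**What to change.** Restate P2 as a patient-level OLS regression of P-SNF placement (yes/no) on case-manager condition, with standard errors clustered by case manager. This matches P7 and the SAP's default for binary outcomes, estimates the stated difference in proportions directly, weights by patients, and has no difficulty with managers at 0% or 100%. A size-weighted or beta-binomial analysis of each manager's counts would also be acceptable if a manager-level model is preferred, provided that the unit and weights are stated.

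Add the same clustering statement to P1, where the gamma regression of patients' LoS by case-manager arm has the same omission.

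The cost is one sentence for each outcome and a possibly wider interval for P2. Project Status says that outcomes had not been examined by experimental condition, so at the date of the SAP the choice could be fixed without knowledge of the results.

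### P4 and P5 take p-values from manager-clustered standard errors among about 750 responders; if responders concentrate in a few dozen managers, the nominal 5% test rejects about 7-10% of true nulls

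*SAP*

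**What the plan says.** The SAP's Randomization section makes the case manager the unit allocated to Default List or P-SNF Top-Sorted List. Project Status counts 104 active managers in the top-sorted arm and 70 in the default arm on 1/2/23.

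The outcomes concerned compare those two arms:
- **P4** uses a negative binomial model, whose purpose is given as: "test whether the number of P-SNFs selected differs as a function of case manager condition, clustering standard errors at the case manager level".
- **P5** is a beta regression on the percentage of patients choosing at least one P-SNF, with the same clustering.
- **P3** is a negative binomial regression to "test whether the number of P-SNFs preselected differs as a function of case manager study arm", and **S1** is an OLS regression on minutes. Both are clustered by case manager.

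The notes under P4 and P5 warn that "only ~15% of patients indicate their selections in the Repisodic app" and that the analysis will use those with data. P3 and S1 carry no such note.

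The SAP does not name a reference distribution (z or t), a finite-sample correction or a randomisation-based test. The fallback in Analysis Approach promises other tests suited to the outcome's distribution. It does not address data concentrated in a few managers.

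**The concern.** A cluster-robust test holds its size when many clusters each supply a small share of the information. What counts is the effective number of clusters, which falls when some are much larger than others. When it is low, the usual clustered standard error tends to be too small and a z or t(G-1) reference too narrow.

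P3 and S1 draw on all patients of all 174 managers. P4 and P5 draw on about 0.15 × 5,000 = 750 responders, or 750/174 = 4.3 per manager on average. Whether a choice is entered in the app could well depend on how the manager uses the app with patients. If so, some managers would supply many responders and others almost none.

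P4 and P5 are both primary outcomes. At stake is a false-positive rate above the .05 used in the Power Analysis section, in addition to any multiplicity across the eight primary outcomes.

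**Working it through.** **1. The plan's own figure.** The SAP states: "We expect to have 80% power to detect a 4% increase (34% to 38%) in selection of P-SNFs at two-tailed p < .05". Splitting 5,000 patients 70:104 gives n₁ = 5,000 × 70/174 = 2,011.5 and n₂ = 2,988.5. The pooled proportion is 0.3639.
- SE under the null = √[0.3639 × 0.6361 × (1/2,011.5 + 1/2,988.5)] = 0.01388.
- SE under the alternative = √(0.34 × 0.66/2,011.5 + 0.38 × 0.62/2,988.5) = 0.01380.
- Power = Φ[(0.04 − 1.96 × 0.01388)/0.01380] = Φ(0.93) = 82.3%.

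A continuity correction gives 81.5%, and an ICC of 0.002 gives 80.3%. The 80% is therefore reproduced to within about 2 points. It refers to 5,000 patients and says nothing about the size of the P4 and P5 tests.

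**2. Effective managers among responders.** Let G = 174, n̄ = 5,000/174 = 28.7 patients per manager and p = 0.15. Assume a caseload CV of c and a between-manager ICC of ρ for recording a choice; the SAP gives neither. Then approximately

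G_eff = G / [(1 + c²)(1 + ρ(1 − p)/p) + (1 − ρ)(1 − p)/(n̄p)],

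with (1 − p)/p = 5.667 and (1 − p)/(n̄p) = 0.85/4.31 = 0.197.

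| c | ρ | Denominator | G_eff |
|---|---|---|---|
| 0 | 0 | 1.197 | 145 |
| 0 | 0.1 | 1.567 + 0.178 = 1.744 | 100 |
| 0 | 0.3 | 2.700 + 0.138 = 2.838 | 61 |
| 1 | 0 | 2.000 + 0.197 = 2.197 | 79 |
| 1 | 0.1 | 3.133 + 0.178 = 3.311 | 53 |
| 1 | 0.3 | 5.400 + 0.138 = 5.538 | 31 |

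Simulated values at ρ = 0 were about 141 (c = 0) and 81 (c = 1), so the approximation serves.

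**3. Type I error against effective managers.** Null simulations used 3,000 data sets per setting (Monte Carlo error about √(0.05 × 0.95/3,000) = 0.4 points). They had 70 and 104 managers, 750 responders and log-normal numbers per manager. Outcomes were negative binomial counts with between-manager gamma variance of 0.1 or 0.3 (assumed). The ranges below cover z and t references and both variances.

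| Effective managers (approx.) | Rejection at nominal 5% |
|---|---|
| 141 | 5.2-5.9% |
| 118 | 5.4-6.4% |
| 81 | 5.6-6.0% |
| 57 | 6.3-7.8% |
| 43 | 7.4-8.0% |
| 30 | 8.8-10.5% |

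Step 2 puts manager-dependent recording at roughly 30-60 effective managers, except where caseloads are even and dependence is weak. Simulating the dependence directly (ρ of 0.1-0.3) gave 7-10%. A separate set with a yes/no outcome, closer to P5, used ρ of 0.1-0.5 and caseload CVs of 0.7-1.8. It gave 5.6-11.8%, mostly 6.5-8.5%. Using t(G-1) in place of z lowers the error by only 0.1-0.5 points.

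**4. P3 and S1, all 5,000 patients.** Even caseloads gave 4.5-5.2% (P3) and 5.6-6.1% (S1). At CV 1 the range was 5.9-7.0% in these runs, and about 5-6% in a further simulation with staggered account creation and CV up to 1. At CV 3 it was 9.5-10.7%, with about 31 effective managers of 174.

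**5. Re-randomisation over managers.** A studentised permutation of arm labels rejected 4.2-5.6% of true nulls in the 174-manager settings where it was run. With responders confined to 25-174 managers it rejected 4.3-5.8%.

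**The case against.** The strongest reply is that the SAP does the standard thing: it clusters at the randomised unit with 104 + 70 = 174 clusters, which is ample. That stands for P3 and S1.

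A reader might infer that every manager-level test here runs at 6-12%. The documents do not support this. They give no caseload distribution and no outcome ICC, and nothing suggests the concentration needed for about 12%, which is roughly 24 effective managers of 174.

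A reader might also infer that the 15% response rate itself causes the inflation. It does not. At caseload CV 2, 750 responders spread like the caseload gave 7.9%, against 8.3% for all 5,000 patients. The low rate matters only if recording varies by manager, which the SAP does not say. The 15% is also a pre-study figure.

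Nor does the SAP commit to a large-sample z test. It is silent on z or t and on any correction, so a corrected standard error would fit its wording for OLS.

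Finally, the re-randomisation test is not a complete cure. Recording happens after randomisation, so the test is exact only under the null that arm affects neither response nor outcome. It does not remove selection bias from a responders-only comparison. Paired with a model-based interval, it can occasionally disagree with that interval.

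**Conclusion.** The point holds in a conditional form and is a refinement, not a serious flaw. If recording a selection depends on the manager, the planned P4 and P5 tests reject about 7-10% of true nulls at a nominal 5%, and the lower half of that range is the better supported. If it does not, the error is about 5-6% at even to moderately uneven caseloads. P3 and S1 are adequate as planned, at about 5-6%, unless caseloads are extremely uneven.

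The result rests on assumed response ICCs, caseload CVs and between-manager outcome variance. For P5 it rests on a yes/no outcome as a stand-in, since the beta regression itself was not simulated. The recommendation depends less on these assumptions, because re-randomisation stayed near 5% wherever it was tried.

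**What to change.** Keep the stated regressions for the estimates. For P4 and P5, take the p-value from a studentised re-randomisation test:
- Permute Default and Top-Sorted across case managers with the arm counts fixed.
- Use the arm coefficient divided by its manager-clustered standard error as the statistic.
- State that this assumes simple randomisation of managers, consistent with the SAP's account of a chance imbalance, and that being active did not depend on arm.

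Offer the same test as an optional sensitivity analysis for P3 and S1. Where available, give a small-sample-corrected interval (CR2-type with Satterthwaite degrees of freedom), and otherwise name the reference distribution. Report patients and responders per manager by arm, so that the effective number of managers can be seen.

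The SAP says outcomes had not been examined by condition, so this could be fixed without knowledge of results. It costs a few sentences and a short script, with slightly wider intervals and slightly lower nominal power. The SAP should also state the limit on exactness when arm affects response.
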